Complete Title of Protocol: Exercise Snacks and Glutamine to Improve Glucose Control in Adolescents with Type 1 Diabetes

NCT: NCT03199638

Date: April 24, 2015

RESEARCH PLAN

I. Specific Aims : To determine whether the sustained use of short bouts of exercise ('exercise snacks'), with or without the administration of the amino acid glutamine results in diminished glycemic variability and/or improved glucose control in adolescent with T1 diabetes.

II. Background and Significance: Puberty is associated with a physiological decline in insulin sensitivity [1,2] and such a decline leads to increased difficulty in achieving glycemic control in adolescents with T1D [3,4]. Designing innovative ways to improve diabetes control in adolescents is a highly desirable and challenging goal. Exercise increases glucose uptake by skeletal muscle [5,6], through an insulin-independent mechanism [7,8], and exercise training increases mitochondrial biogenesis and therefore muscle respiratory capacity and the expression of GLUT-4, the main glucose transporter in skeletal muscle [9]. Literature suggests exercise improves glucose tolerance in healthy individuals [10], and increases insulin sensitivity as measured by the euglycemic clamp in adolescents with T1D [11]. A recent meta-analysis concluded that regular aerobic training improves HbA1c in patients with T1D [13]. Nutritional supplements are critical for conditions of malnutrition caused by either decreased intake or chronic medical illnesses. Diabetes, especially when poorly controlled, is a state of relative malnutrition with impaired glucose transport and relatively decreased amino acid flux. We have previously shown that oral supplementation with glutamine, a non essential amino acid dietary supplement given prior to exercise decreases overnight post-exercise blood glucose in adolescents with long-standing T1D who do not retain residual insulin secretion [17,18]. These data suggest that a simple dietary supplement may be beneficial improving diabetes control. Using hyperinsulinemic euglycemic clamps we further examined whether this effect of glutamine was secondary to increased insulin sensitivity in adolescents with T1D (Torres-Santiago, et al, manuscript to be submitted). Lack of time is the most commonly perceived reason preventing the performance of exercise in both healthy and diabetic subjects [14,15]. Recently, [name], an Australian scientist who will serve as a consultant in this grant and colleagues, showed that performing 6 bouts of just x1 min of intense exercise (90% maximal heart rate; termed 'exercise snacks') 30 min before meals, improved glycemic control in obese adults with impaired glucose tolerance [16]. This novel approach is particularly attractive due to its simplicity and low cost, but this has never been investigated in adolescents with T1D previously.

III. Preliminary Studies/Progress Report (Not to exceed 3 pages.)

a). Pilot studies on the effect of glutamine and exercise in adolescents with T1D [17]. Maura, et al, Diabetes Care 2011.

[figure not shown]
Post-exercise hypoglycemia is a common problem in youth with T1D. Approximately 20% of endogenous glucose production comes from gluconeogenesis via amino acid (AA) precursors, particularly GLN and AA depletion occurs in insulin-induced hypoglycemia. As GLN is a major contributor to gluconeogenesis, we studied the effects of GLN on glucose concentrations during afternoon exercise as well as overnight post exercise. We studied ten adolescents with uncomplicated T1D (mean age 15 ± 1 yr-old, 5M, 5F) who had been diabetic for 6.2 ± 3.3 years and wore insulin pumps, with a mean HbA1c of $6.9\pm0.9\%$, and a normal BMI (between the 10th and 85th percentiles). They were on no chronic medications.

Subjects were studied twice in the Clinical Research Center CRC during 1-h exercise session starting at 3PM. Mean blood glucose was in the mid 100 mg/dL range prior to exercise. Sessions consisted of 4, 15-min treadmill exercise (heart rate 140 bpm) with 5-min rest breaks interspersed. Blood glucose was continuously monitored during exercise and overnight. Basal insulin rates were continued during the study. Subjects were randomized to receive a drink containing either glutamine (before exercise and at bedtime (0.5 g/kg per dose), or a calorie- and nitrogen-free placebo. Studies were repeated within 3 weeks, and in randomized order. Plasma GLN concentrations measured 16 h post exercise the following morning were higher during the GLN study day than after placebo (316 vs. 200 μ mol/L, $p<0.001$).

However, regardless of the dietary supplement received prior to exercise, plasma GLN concentrations measured in the postabsorptive state the following day, were below normal as compared to healthy, age-matched controls measured at rest ($p<0.001$) [33]. In earlier studies performed under resting conditions and using the same assay, we consistently observed that adolescents with T1D had plasma GLN concentrations in the normal range at rest as normal age-matched controls (484 ± 25 vs. 513 ± 29 μ mol/L, NS) [33]. This suggests that intense exercise likely depletes plasma GLN in adolescents with T1D, as it does in healthy adults. Blood

glucose was similar at baseline on both study days (143 ± 31 and 162 ± 54 mg/dL on the GLN and placebo study day, respectively; $p=0.44$), and blood glucose dropped comparably ($52 \pm 15\%$ vs. $52 \pm 9\%$ on the GLN and placebo study day, respectively; $p=0.84$) during exercise on both days. Yet overnight, post-exercise low blood glucose levels (defined as either <70 mg/dL or <60 mg/dL) were significantly more frequent ($P=0.03$, and 0.05 , respectively) after GLN than after placebo. The cumulative probability of overnight hypoglycemia was increased on the GLN day (80%) compared with placebo (60%, $p=0.02$, Fig 4). We concluded that GLN supplementation increases the incidence of post exercise nighttime hypoglycemia. [17]. Taken in aggregate, our preliminary studies suggest that, in adolescents with T1D performing heavy exercise, plasma GLN is low after exercise; and GLN supplementation increases the likelihood of hypoglycemia after exercise. As the patients studied presumably had no residual endogenous insulin secretion, our findings suggest that GLN may enhance glucose uptake and/or increase insulin sensitivity. These data, in addition to the data reviewed from other studies suggest that GLN supplementation may affect insulin sensitivity either at the peripheral or hepatic level in T1D. If proven true, these results could have important implications to improve glycemic control in T1D.

Fig.4 Time to post-exercise, nocturnal hypoglycemia (defined as first drop below 70mg/dL) in adolescents with T1DM after oral ingestion o glutamine or placebo [17]

b). Glucose-lowering Effects of Glutamine in Adolescents with Type I Diabetes [18] Torres, et, al (manuscript to be submitted for publication)

Thirteen pubertal adolescents (15.96 ± 1.6 years [SD], 8M; 5F; BMI $69^{\text{th}} \pm 16$ centiles 6, HbA1C $8.2 \pm 0.5\%$, T1D: 7.5 ± 4 yrs) on insulin pumps were randomized to receive a drink with GLN or placebo pre-exercise, bedtime and early morning (0.25 g/kg/dose) in a double-blind crossover design over 4 weeks. Exercise session (3pm) consisted of four 15-min treadmill/5-min rest cycles. Blood glucose (BG) was monitored during exercise and overnight. The following morning, a 5-hr primed, continuous infusion of D-[6, 6- $^2\text{H}_2$] glucose was administered, during a 2-dose hyperinsulinemic, euglycemic clamp (low dose: $8 \text{ mU/m}^2/\text{min}$; high dose: $80 \text{ mU/m}^2/\text{min}$) in the post absorptive state. BG levels dropped comparably during exercise on both days. However, the total number of nocturnal hypoglycemic events (17 vs. 7, $p=0.045$) and the cumulative probability of overnight hypoglycemia (50% vs. 33%, ($p=0.02$) were higher on the glutamine day than on the placebo day. During clamp, glucose infusion rate did not differ between days ($7.7 \pm 1 \text{ mg/kg/min}$ vs. $7.0 \pm 1 \text{ mg/kg/min}$; glutamine vs. placebo; $p=0.4$). A correlation was noted between nocturnal hypoglycemic events and S_I on the glutamine day.

Our findings confirm our previous observations that glutamine has glucose-lowering effects in adolescents with type 1 diabetes after exercise no consistent change in insulin sensitivity was observed. Although a correlation was noted between nocturnal hypoglycemic events and insulin sensitivity on the glutamine day. The mechanisms mediating the effect of glutamine remain to be elucidated.

C). 'Exercise snacks' before meals to improve glycemic control in individuals with insulin resistance [16]. Francois, et al, Diabetologia, 2014

[figure not shown]

There were 3 groups 1) SIT: uninterrupted sitting (control); 2) LW: sitting + 3 min bouts of light-intensity walking at 3.2 km/h every 30 min; and 3) SRA: sitting + 3 min bouts of simple resistance activities (alternating half-squats, calf raises, brief gluteal contractions and knee raises) every 30 min (see below).

Simple Resistance Activities – SRA's

Over 22 h, both LW and SRA significantly reduced mean [interstitial] glucose, time in hyperglycemia and glycemic variability (quantified via the SD of mean glucose and mean amplitude of glycemic excursions) relative to uninterrupted sitting (Table). These simple interruptions to sitting significantly reduced the time in hyperglycemia, mean glucose and glycemic variability in adults with T2D. **This approach has not been studied yet in adolescents with type 1 diabetes.**

Table (A) Participant Characteristics and (B) Effects of the Three Trial Conditions on Glycemic Control

(A) Participant characteristics		(B) Effects of the three trial conditions on measures of glycemic control over 22 h			
Characteristic	N or mean (95% CI)	Measure of glycemic control	SIT (control)	LW	SRA
Number of study participants	14 M 10 F	Time in hyperglycemia (%)	60.3 (49.2, 71.3)	37.5 (26.5, 48.6)**	26.5 (15.5, 37.6)**
Age (yr)	62.3 (64.8, 59.8)	Time in hyperglycemia (hr)	13.3 (10.8, 15.7)	8.3 (5.8, 10.7)**	5.8 (3.4, 8.3)**
BMI (kg/m ²)	33 (34.4, 31.7)	Mean interstitial glucose (mg/dl)	11 (10.2, 11.8)	9.4 (8.5, 10.2)**	8.6 (7.8, 9.4)**
HbA1c (%)	7.2 (7.5, 7)	SD of mean interstitial glucose	2.2 (2, 2.5)	1.9 (1.7, 2.2)**	1.7 (1.5, 2)**
Note: All participants were Metformin/diet controlled individuals with type 2 diabetes.		MAGE (mg/dl)	104.94 (92.11, 117.78)	85.5 (72.66, 98.34)**	76.18 (63.35, 89.02)**
SD=standard deviation; MAGE=mean amplitude of glycemic excursions. *difference from SIT ($P < 0.05$); **difference from SIT ($P < 0.001$); Analysed using multi-level mixed models, controlling for age and BMI. Data are mean (95% CI).					

IV. Research Design and Methods

In this protocol we will determine whether 'exercise snacks', alone or in combination with dietary glutamine supplementation over a period of 3 months improve glycemic control in adolescents with type 1 diabetes.

Inclusion/Exclusion Criteria:

Twenty-four adolescents with T1D for at least 12 months, between 13-19 yr-old will be recruited after informed written consent from their parents and the youngsters themselves. We will strive to recruit patients with comparable phenotype in both groups. They will be of normal weight (BMI between 10th and <85th percentile) and will be in puberty (at least Tanner stage III breast or genitalia) with a HbA1c between 7.5 and 9%. Subjects will be on either multiple daily injections (MDI) or insulin pump therapy. They will be recruited among the ~1,000 patients with T1D followed at Nemours Children's Clinic Jacksonville. We will exclude subjects with biopsy proven celiac disease, cystic fibrosis, chronic steroid therapy, mental retardation, microalbuminuria or evidence of other diabetic complications. Subjects involved in an active exercise program or in an organized sport team will be excluded. Studies will be conducted at least 2 weeks after resolution of any intercurrent infection.

Procedures: All subjects will have a full physical exam including Tanner staging as well as waist circumference measurement. A HbA1c, will be obtained as well as fasting triglycerides. A continuous glucose monitor (CGM iPro®, Medtronic Minimed, or a DexCom ^4) will be worn blindly for 6 days and data downloaded. Subjects will then be randomized to 2 study groups of 12 patients each:

(A) an 'exercise group', in which subjects will perform daily 'exercise snacks' within 30 min before breakfast, lunch, and/or dinner or bedtime snack, along with a placebo drink;

(B) an 'exercise + glutamine group', in which subjects will receive a glutamine drink (0.25 g/kg per dose) before meals TID, and perform 'exercise snacks' before each meal.

[figure not shown]
Allocation to the exercise only or the exercise + glutamine group will be stratified according to HbA1c range (eg, 7.5-7.9%; 8.0-8.4%; 8.5-9.0%), so as to ensure the comparability of groups.

The placebo and glutamine drink will be prepared at home using measuring spoons of glutamine or placebo powder to be mixed in a calorie-free, flavored soft drink tailored to the child's individual taste. Patients, families and investigators will be blinded as to the contents of the supplement.

Exercise snacks will be designed to be feasible using 6 min worth of simple resistance activities (SRA's) designed by the exercise physiology consultants, Drs. [name] and [name]. These will consist of activities such as alternating half-squats, calf raises, brief gluteal contractions and knee raises. A short video will be created showing the participants how to conduct these exercises and these will be updated periodically in order to keep their interest and compliance. We elected not to use an accelerometer as the data to be gathered from these would be less useful for the study given the short nature of these bouts of exercise. These will be completed 30 min before breakfast, lunch and dinner.

Patients will keep a record of their dietary intake and physical activity for 2 days while CGM is placed (one weekday+ one weekend day) at baseline, and at 1, and 3 months during the study. If the family has a smart phone, a free application will be installed which is "My diet diary calorie count" for better assessment of total caloric intake during this study. Otherwise, a log book would be used. Compliance will be monitored by weekly contact with the study subjects either via phone call or text messaging or via MyNemours. A system of rewards will be implemented with a \$10 gift card given per week with at least 50% compliance with study program, with an extra \$25 for successful wearing and downloading of the CGM at baseline and 3 months ($\$10 \times 12w = \120 , $+\$25 \times 3 = \75 , Total = \$195 per subject).

At one month visit after the enrolment, CGM will be placed again for 6 days, then all baseline studies, including CGM, HbA1c and triglycerides will be repeated at 3 months. Every patient will undergo a body composition analysis using a dual X-ray absorptiometry (DEXA) at the end of the study. Total insulin dosing will be carefully recorded as units/kg/day during the study.

- Assays – HbA1C will be measured using a DCA 2000 in clinic [17,18]. Triglycerides (TG) will be performed using an Olympus AU400e Chemistry.

-Calculations - An insulin sensitivity score (ISS) will be calculated as previously described using the SEARCH ISS model: $\log_e IS = 4.64725 - 0.02032(\text{waist, cm}) - 0.09779(\text{HbA1c, \%}) - 0.00235(\text{TG, mg/dl})$ ($R^2=0.74$ in the initial SEARCH model) [34-35]. This has been validated using the hyperinsulinemic euglycemic clamp, considered the gold standard for insulin sensitivity measures [34,35]. CGM data will be downloaded and used to calculate % blood glucose (BG) at, below or above target and the mean amplitude of glycemic excursions using a SAS program (MAGE) as previously described [17,21,22].

-Statistical Analysis and Statistical Power.

To determine whether short bouts of exercise and/or glutamine improve glycemic variability and diabetes control, we will compare the following parameters between baseline and 3 months:

- a) Changes in HbA1C
- b) Changes in MAGE
- c) Changes in % BG at target (70-180), below target (<70), above target (>180)
- d) Changes in ISS
- e) Changes in total insulin dosing (units/kg/day)

A mixed effects models and/or generalized estimating equations (GEE), which ever appropriate will be used within and between subjects and groups comparisons. Model assumptions will be checked by analyses. Significance will be established at $p<0.05$.

-Sample Size Justification: A sample size of 24 patients is planned assuming no more than 10% attrition rate. The main judgment criterion will be the mean amplitude of glycemic excursion (MAGE, measured using CGM). In the Australian study by Dunstan et al. [36]—described above in the Preliminary results section of this application—performed in adults with type 2 diabetes, MAGE was 104.9 ± 12.8 mg/dl (mean \pm SD) in the sedentary group of patients with type 2 diabetes, vs. 76.2 ± 12.8 mg/dl—i.e., a drop by 28.7—in the group performing short bouts of resistance exercise. To the best of our knowledge, there is no earlier study of such type of exercise in adolescents with T1D published in literature. Assuming ‘exercise snacks’ will decrease MAGE to the same extent in our population of children with T1D as in adults with T2D, such reduction will amount to an effect size of $\delta/\sigma=28.7/12.8 \approx 2.24$, where δ is the expected change in MAGE ($104.9-76.2=28.7$), and σ^2 the estimated variance of MAGE ($\sigma=12.8$, calculated based on [name] et al’s data). Using equations for unpaired studies, the number (n) of subjects per group needed to detect such difference with an α risk <0.05 , and a statistical power($1-\beta$) of 80% can be estimated as: $n= 2 \times (Z_\alpha + Z_\beta)^2 / (\delta^2/\sigma^2)$ [37], where $Z_\alpha=1.96$, and $Z_\beta=0.84$, therefore $n=2 \times (1.96 + 0.84)^2 / (2.24)^2 = 2 \times 7.84/5.02=3.1$. The enrolment of 12 patients per group therefore should be amply sufficient to test our hypothesis, even if we take into account a putative 25% attrition rate.

- Future Directions: These simple and short resistance activities as it was shown in previous studies [16, 36] have significantly reduced the time in hyperglycemia, mean glucose and glycemic variability in adults with T2D. With the ubiquity of sedentary behaviors and the low adherence to structured exercise, this approach has the potential to be beneficial and practical. This interesting approach has not been studied yet with combination of glutamine in patients with type 1 diabetes.

V. Facilities Required/Physical Location of Study

This study will be performed in outpatient settings and will recruit patients who are followed at the deivision of Endocrinology at the Nemours Children’s Healthy System in Jacksonville.

VI. References

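### Both in-house studies report more post-exercise nocturnal hypoglycaemia on glutamine, yet the eligibility criteria do not address patients prone to hypoglycaemia

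*Combined protocol and SAP*

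**What the plan says.** Section III a) summarises a crossover study in ten adolescents with T1D: "We concluded that GLN supplementation increases the incidence of post exercise nighttime hypoglycemia". The figures are given as "The cumulative probability of overnight hypoglycemia was increased on the GLN day (80%) compared with placebo" (60%, p = 0.02).

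Section III b) summarises a second crossover study, in thirteen adolescents. It reports that "the total number of nocturnal hypoglycemic events (17 vs. 7", p = 0.045) was higher on the glutamine day, with cumulative probabilities of 50% and 33% (p = 0.02).

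Section IV, Inclusion/Exclusion Criteria, sets limits on age, diabetes duration, BMI, pubertal stage and HbA1c (7.5 to 9%), and accepts pump or multiple-injection therapy. The exclusions are: "We will exclude subjects with biopsy proven celiac disease, cystic fibrosis, chronic steroid therapy, mental retardation, microalbuminuria or evidence of other diabetic complications". A further sentence adds: "Subjects involved in an active exercise program or in an organized sport team will be excluded". Studies must also fall at least two weeks after any infection has resolved. Nothing else bears on entry.

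Section IV, Procedures, has a blinded 6-day CGM wear whose data are downloaded before randomisation to two groups of 12. Group B takes glutamine 0.25 g/kg before meals three times a day, with the drink made up at home, and exercises before each meal for 3 months. Weekly contact is described as a check on compliance. CGM is placed again for 6 days at one month and repeated at 3 months. Under Statistical Analysis, percent of glucose below 70 is compared between baseline and 3 months.

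**The concern.** The preliminary data identify one specific hazard of the study supplement, and the trial's rationale draws on the same glucose-lowering effect. One would expect the entry criteria to respond to it. They deal with celiac disease, cystic fibrosis, steroids, microalbuminuria and sport, but not with a patient who recently had a severe low or who does not feel lows coming. Such a patient, if otherwise eligible, can be enrolled and has an even chance of receiving glutamine for 3 months.

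In the pilots glucose was monitored through the night after the exercise session. Here exposure is daily and at home, and the weekly contact is not described as looking for hypoglycaemia. What is at stake is the safety of a small, identifiable subgroup of minors.

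**Working it through.** The plan has no design figure for this point, so the check compares sections III and IV and asks how firm the pilot figures are.

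**1. Study (a).** The difference is 80 − 60 = 20 percentage points. Read as simple proportions of ten patients, this is 8 against 6, a difference of two patients. Simple tests give p = 0.63 (Fisher) and p = 0.50 (exact McNemar with discordant pairs 2 and 0). The stated p = 0.02 therefore presumably comes from the time-to-event analysis shown in the figure.

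**2. Study (b).** The ratio of events is 17/7 = 2.43. Given 17 + 7 = 24 events and equal exposure on the two days, the glutamine count is Binomial(24, 0.5) if there is no effect.
- Normal approximation: z = (17 − 7)/√24 = 2.04, p = 0.041.
- Mid-p: p = 0.043. Exact two-sided: p = 0.064.
- The stated 0.045 is close to the first two; the test is not named.
- Exact 95% limits for 17/24 = 0.71 are 0.489 and 0.874. As ratios, π/(1 − π), these become about 0.96 and 6.9.

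These calculations ignore clustering of events within patients. The number of nights is also unclear: 50% and 33% of 13 are 6.5 and 4.3, whereas 6/12 and 4/12 would fit. I therefore give no rate per night.

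**3. Pilots against this trial.**

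| | Study (a) | Study (b) | This trial, group B |
|---|---|---|---|
| Per dose | 0.5 g/kg | 0.25 g/kg | 0.25 g/kg |
| Timing | before exercise, bedtime | before exercise, bedtime, early morning | before meals, three times a day |
| Exercise | four 15-min treadmill bouts | four 15-min treadmill bouts | 6-min resistance bouts |
| Glucose watch | continuous, in exercise and overnight | in exercise and overnight | study CGM in short windows |
| Insulin delivery | pump | pump | pump or injections |
| HbA1c | 6.9 ± 0.9% | 8.2 ± 0.5% | 7.5 to 9% at entry |

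Study (b) matches the trial in amount per dose and in HbA1c. Neither pilot matches it in dose timing or exercise.

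**4. CGM coverage.** Three wears of 6 days make 18 days, of which 12 fall after randomisation (assuming the last wear is also 6 days and on treatment). That is 12/84 = 14% to 12/91 = 13% of the treatment period.

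**5. Chance of enrolling such a patient.** The documents give no prevalence, so this rests on an assumption. If a share q of otherwise eligible patients had recent severe hypoglycaemia or unawareness, the chance of at least one among n is 1 − (1 − q)^n.

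| q (assumed) | glutamine group, n = 12 | whole trial, n = 24 |
|---|---|---|
| 2% | 22% | 38% |
| 5% | 46% | 71% |
| 10% | 72% | 92% |
| 20% | 93% | 99.5% |

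This takes recruitment as unselected with respect to hypoglycaemia history.

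**The case against.** The strongest reply is that the pilot risk may not transfer. Both pilots gave a bedtime dose, which matters for events at night, and both used much longer exercise; study (a) also used double the amount per dose. The ratio is imprecise and its exact interval includes 1. All of this stands, and it limits what can be said about size. It does not remove the direction, on which both summaries agree and which the protocol states as its own conclusion for study (a).

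Second, the last item of the main exclusion sentence, on other complications of diabetes, could be read to cover unawareness, and a single clinic recruiting its own patients may apply sensible discretion. That is possible. But the item follows microalbuminuria and says nothing about hypoglycaemia, so a written criterion is still needed for consistent application.

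Third, patients are not cut off: there is weekly contact and a one-month visit, and nothing says that usual home glucose testing stops. That also stands.

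A reader might infer stronger things that the documents do not support:
- That patients spend 3 months on a CGM they cannot see. The CGM is worn in short windows, and blinding is written only for the baseline wear.
- That severe events will be more frequent on glutamine. Study (a) counted glucose below 70 or 60 mg/dL, study (b) gives no threshold, and neither summary reports a severe event.
- That such events would distort MAGE or retention between arms. No figure supports this.
- That the pilot event ratio can be projected over the trial's nights. The differences in dose timing and exercise rule that out.

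**Conclusion.** The point holds as a gap between sections III and IV: the protocol reports a hazard of its own supplement in two studies, and the eligibility text does not address the patients most exposed to it. It is a matter of patient safety at entry. It is not an error in the analysis or the sample size.

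The size of the excess risk under pre-meal dosing and 6-minute bouts cannot be stated from the documents. The chance of enrolling at least one such patient on glutamine runs from 22% to 93% over assumed prevalences of 2% to 20%.

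The conclusion rests on the eligibility paragraph being the full set of entry rules and on the pilot direction carrying over. It makes no claim about safety monitoring in consent material, which is not part of the public text. Because the change is cheap and the hazard is the protocol's own, it should be made.

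**What to change.** Reconcile the eligibility text in section IV with the findings in section III a) and b). Add an entry criterion that covers recent severe hypoglycaemia and known hypoglycaemia unawareness. The definition and the look-back period are for the investigators to set; none is proposed here. If they consider that the existing item on diabetic complications already covers these patients, the text should say so.

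The baseline CGM is already downloaded before randomisation, so it can be reviewed for this purpose with no added procedure. State in Procedures that this review takes place before allocation.

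The cost is one line of eligibility text, a look at data in hand, and a few more screen failures. Their number cannot be estimated, because the roughly 1,000 clinic patients are counted before the HbA1c, BMI, puberty and exercise criteria apply. The result will also not cover the highest-risk patients, which the report should state. Dosing and care during the trial are not touched.

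### The change in MAGE, the main criterion, is compared with no baseline-MAGE term, while allocation balances only HbA1c: adjust for baseline MAGE in the model

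*Combined protocol and SAP*

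**What the plan says.** Section IV, Procedures, has the CGM worn before allocation: it "will be worn blindly for 6 days and data downloaded". The next step is "Subjects will then be randomized to 2 study groups of 12 patients each". On how patients are allocated it says: "Allocation to the exercise only or the exercise + glutamine group will be stratified according to HbA1c range". HbA1c range is the only stratifier. Three ranges are given as an example, and the purpose is "so as to ensure the comparability of groups".

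Sample Size Justification says: "The main judgment criterion will be the mean amplitude of glycemic excursion". Under Calculations, MAGE is derived from the downloaded CGM data by a SAS program; when this is done relative to allocation is not stated.

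The statistical section lists the outcomes compared between baseline and 3 months. HbA1c comes first, followed by "b) Changes in MAGE". The method is a mixed model or GEE, whichever suits. Neither baseline MAGE nor the HbA1c stratum is named as a model term.

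**The concern.** The plan wants comparable groups but secures comparability on a variable other than its main criterion, and the analysis does not make up the difference. HbA1c reflects average glucose, whereas MAGE measures the size of swings. Balancing the first balances the second only so far as the two correlate, and the document gives no correlation.

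In a trial of 24, the arms can therefore start apart on MAGE. The arm that starts higher tends to fall further by regression to the mean. In an unadjusted comparison of changes, part of that fall is credited to, or taken from, glutamine. At stake are the precision of the main result and how it can be read after an unlucky draw.

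**Working it through.** **1. The plan's own figure.** Inputs from Sample Size Justification: difference 28.7 mg/dl, SD 12.8, z values 1.96 and 0.84. n = 2 × (1.96 + 0.84)² / (28.7/12.8)² = 3.1 per group, as stated. The present point leaves this figure unchanged.

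**2. Size of the chance gap.** Without a useful stratifier, the SE of the between-arm difference in mean baseline MAGE is SD × √(2/12) = 0.41 SD. The probability of a gap above 0.5 SD is 2 × [1 − Φ(0.5/0.408)] = 22%. Simulation of 24 patients in three strata gives:

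| Stratifier | Assumed HbA1c-MAGE correlation | SD of gap | P(gap > 0.5 SD) |
|---|---|---|---|
| HbA1c | 0 | 0.41 | 22% |
| HbA1c | 0.3 | 0.39 | 20% |
| HbA1c | 0.5 | 0.37 | 17% |
| HbA1c | 0.7 | 0.32 | 12% |
| Baseline MAGE, well-centred bands | – | 0.19 to 0.22 | 1 to 2.5% |

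**3. In mg/dl.** With the stated SD of 12.8, one SE is 12.8 × 0.408 = 5.2. The 12.8 also equals the half-width of the source study's 95% interval: (117.78 − 92.11)/2 = 12.8. If that is an ordinary interval on 24 people, the SD is 12.835/1.96 × √24 = 32.1, and one SE is 13.1. That is a separate issue; both values are carried here as a range.

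**4. Effect on a comparison of changes.** With pre-post correlation ρ (assumed), a baseline gap d shifts the expected difference in change by (ρ − 1) × d. For a one-SE gap:

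| ρ | Shift at SD 12.8 (mg/dl) | Shift at SD 32.1 (mg/dl) |
|---|---|---|
| 0.3 | 3.7 | 9.2 |
| 0.5 | 2.6 | 6.5 |
| 0.7 | 1.6 | 3.9 |

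**5. Is the test still valid?** Under HbA1c strata, with correlation 0.3, ρ = 0.5 and no true effect, the unadjusted t-test on changes rejects in 4.7% of simulated trials. That is nominal.

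**6. Gain from adjustment.** In units of the MAGE variance, the per-patient variance is 2(1 − ρ) for change scores. For the adjusted comparison it is (1 − ρ²), times about 1.046 for residual imbalance. At ρ = 0.5 these are 1.00 and 0.75 × 1.046 = 0.785, a cut of 22%. A simulation with the stratum terms included gave 15 to 21% for HbA1c-MAGE correlations of 0.5 down to 0, hence about 20%.

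Power at an assumed effect of 0.9 SD:
- Change score: 0.9/√(1.00/6) = 2.20 on 22 df, giving 56%.
- Adjusted: 0.9/√(0.785/6) = 2.49 on 21 df, giving 66%. In simulation the two stratum terms cost about 1 point or less.
- The same formulas give 43% against 58% at ρ = 0.3, and 78% against 82% at ρ = 0.7.

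**7. Gain from changing the stratifier.** With MAGE strata in place of HbA1c strata, simulated power is about the same unadjusted (55 to 57% either way) and rises from about 66% to 67% adjusted.

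**The case against.** The strongest reply is that nothing here is an error. HbA1c is a listed outcome, enters the insulin sensitivity score, is read in clinic without processing, and belongs to the stated aim of better glucose control. Stratifying on it is a legitimate choice. This stands.

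A reader might infer that chance imbalance would produce a false glutamine effect. The documents do not support that: allocation is randomised, a valid test already allows for such gaps, and the error rate in step 5 is nominal. The shift is real only conditional on an unlucky draw.

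A reader might also infer that MAGE should replace HbA1c as stratifier because it is already in hand. The data are downloaded before allocation, but the document does not say that MAGE has been computed by then. Nor does it give a MAGE distribution in this population from which to set bands; its only MAGE figures come from adults with type 2 diabetes. Bands off-centre by 1 SD give a gap SD of 0.31 and a gap above 0.5 SD in 10% of trials. At 1.5 SD off-centre the figures are 0.36 and 16%, close to HbA1c strata. Crossing three HbA1c ranges with three MAGE bands leaves 24/9, about 2.7 patients per cell.

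Two further replies concern the analysis. A mixed model that constrains the arms to a common baseline mean would adjust implicitly. That is true, but the text does not say so, and an ordinary arm-by-time model reproduces the difference in changes. Also, at the protocol's own effect of 28.7/12.8 = 2.24 SD, power exceeds 99% without adjustment, so the power gain matters only if the effect is smaller relative to the SD. That is correct, but the variance reduction does not depend on the effect size.

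**Conclusion.** The point holds as a gap in the analysis model, not as a fault in the allocation. With HbA1c strata and 12 per arm, a baseline MAGE gap above 0.5 SD is expected in about 17 to 22% of trials. If it occurs, an unadjusted comparison of changes is moved by regression to the mean. Adjustment removes the linear part of this and cuts the variance by about 20%; at an effect of 0.9 SD, power rises from about 56% to 66%.

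These sizes rest on assumptions that the document does not supply: HbA1c-MAGE correlation 0 to 0.5, pre-post correlation 0.5 (0.3 to 0.7 shown), approximate normality, three strata, and an effect of 0.9 SD, which is 28.7/32.1 if the SD is read from the interval. The gain shrinks as the pre-post correlation rises.

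**What to change.** In the statistical section, state that the between-arm comparison of 3-month MAGE is adjusted for baseline MAGE as a continuous covariate and for the HbA1c stratum used at allocation. The cost is one sentence. The baseline value is already collected, so allocation, patients, visits and assays are untouched.

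Optionally, add baseline MAGE to the allocation, for example by minimisation together with HbA1c range. That would require MAGE to be computed before each patient is allocated and a rule for unusable CGM downloads, for about 1 point of power once the model is adjusted. Pre-set MAGE bands are not recommended.
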